11.5.2. Clinical Global Impressions – Severity Scale (CGI-S)

The CGI-S is a clinician-rated assessment of the subject's current illness state on a 7-point scale, where a higher score is associated with greater illness severity. Following a clinical interview, the CGI-S can be completed in 1 to 2 minutes. The CGI-S will be administered by a qualified rater at the site.

11.5.3. Clinical Global Impressions – Improvement Scale (CGI-I)

The CGI-I scale is a standard 7-point scale ([Guy-1976](#)) that requires the clinician to assess how much the subject's overall symptoms have improved or worsened relative to a baseline state. The CGI-I will be administered by a qualified rater at the site.

11.5.4. Brief Negative Symptom Scale (BNSS)

The BNSS is a rating scale to measure the current level of severity of negative symptoms in schizophrenia and schizoaffective disorder ([Kirkpatrick-2011](#)). The measure is comprised of 13 individual items and 6 subscale scores (blunted affect, alogia, avolition, anhedonia, asociality, and distress). The 6 subscale scores provide a summary score and the 13 individual items provide a composite total score (ranging from 0 to 78). Each of the items are scored on a Likert-type 7-point scale from 0 - 6, where values of 0 indicates symptom is absent and a value of 6 means the symptom is a severe form. The number of items varies per subscale. BNSS raters will be required to meet specific training and education criteria before they are certified to rate for this study.

11.5.5. 12-Item Short Form Survey (SF-12)

The SF-12 is a 12-item self-reported questionnaire that is a subset of the SF-36 Health Survey. The survey captures physical and mental health. There are 8 subscales including: Physical functioning, Role-physical, Bodily pain, General health, Vitality, Social Functioning, Role emotional, and Mental health. The responses are reported on a 3- or 5-point Likert scale, depending on the question. The SF-12 uses 2-items each to estimate scores for 4 of the 8 health concepts (physical functioning, role-physical, role-emotional, and mental health). Score for the remaining 4 healthy concepts (bodily pain, general health, vitality, and social functioning) are estimated using 1 item each. Physical Component Summary (PCS-12) and Mental Component Summary (MCS-12) are computed using the scores of 12 questions and range from 0 to 100, where a zero score indicates the lowest level of health measured by the scales and 100 indicates the highest level of health. The SF-12 will be administered by a qualified rater at the site.

11.5.6. Personal and Social Performance Scale (PSP)

The PSP is a 100-point single-item rating scale of personal and social functioning ([Morosini-2000](#)). The rating is based on the assessment of a patient's functioning in four areas: 1) socially useful activities; 2) personal and social relationships; 3) self-care; and 4) disturbing and aggressive behaviors. Higher scores indicate better functioning. Scores of 0-30 indicate poor functioning; scores of 31-70 indicate varying degrees of difficulty; and scores of 71-100 reflect only mild difficulties at most. The PSP will be administered by a qualified rater at the site.

11.5.7. Medication Satisfaction Questionnaire (MSQ)

The MSQ is a single-item, patient-rated questionnaire that requires the subject to use a 7-point, Likert-type scale to rate how satisfied they are with their current antipsychotic medication (antipsychotic medication taken at the time of screening or within 30 days of screening) ([Vernon-2010](#)). The subject will be asked the following question:

- “Overall, how satisfied are you with your current antipsychotic medication”

Subjects will select 1 of 7 potential responses based on their level of satisfaction from (1) extremely dissatisfied to (7) extremely satisfied as follows:

- (1) Extremely dissatisfied
- (2) Very dissatisfied
- (3) Somewhat dissatisfied
- (4) Neither dissatisfied nor satisfied
- (5) Somewhat satisfied
- (6) Very satisfied
- (7) Extremely satisfied

11.5.8. Healthcare Resource Utilization

Healthcare resource utilization will be assessed by recording the following at Baseline:

- Number of physician office visits, emergency room visits, and hospitalizations (total number and number related to schizophrenia) in the previous 3 months
- Length of each hospital stay in the past 3 months
- Employment status in the past 3 months
- The average number of hours a caregiver(s) spends helping the subject per week (past 3 months)

Healthcare resource utilization will be assessed by recording the following post Baseline:

- Number of physician office visits, emergency room visits, and hospitalizations (total number and number related to schizophrenia) since prior assessment
- Length of each hospital stay since prior assessment
- Employment status since prior assessment
- The average number of hours a caregiver(s) spends helping the subject per week (since prior assessment)

[figure not shown]
11.5.9. Nicotine Use Information

Information regarding the subject's nicotine use will be recorded in the eCRF. Data collected will include the type of nicotine used, approximate amount and time period during which nicotine was / is being used.

11.6. Pharmacokinetic Assessments

All blood samples for determination of plasma SEP-363856 concentrations will be obtained at the same time that other blood samples are taken whenever possible. Date and time of sample collection as well as date and time of the previous dose of study drug prior to pharmacokinetic (PK) blood sampling and the date and clock time of blood sampling, must be recorded. Plasma SEP-363856 concentrations will be determined by a validated liquid chromatography-tandem mass spectrometry (LC-MS/MS) method. Population pharmacokinetics (POPK) analysis will be performed using plasma SEP-363856 concentrations; the results of which will be reported separately. The relationship between PANSS total score and plasma SEP-363856 exposure will be explored using population PK/pharmacodynamics (PD) methods and reported separately. See [Section 24](#), Appendix V for details including instructions of processing blood samples for plasma.

Plasma samples collected for PK concentration analysis CCI 

CCI 

CCI

11.8. Tokenization

The participant will be asked for optional consent to allow access to their medical data.

To allow the linking of subject participants records from different sources, ie, data collected as part of the study as specified in this Protocol and longitudinal real-world data such as electronic health record, claims, and laboratory data from other care settings, without compromising the participant's confidentiality, tokenization and matching procedures will be utilized for US participants only. The tokenization process starts with each data provider generating a token behind the firewall via proprietary software. Personal information such as names and dates of birth from study participants are removed from real-world data sources and replaced with encrypted, one-way, hashed identifiers, and then further encrypted using asymmetric keys in compliance with Health Insurance Portability and Accountability Act (HIPAA). This encrypted information is sent for matching to the anonymized participant master index. While it is not possible to reverse the hash, source-specific tokens can be decrypted and re-encrypted so that records can be linked across sources. The result of the process is a unique anonymized identifier for each participant, which can be used to link participant records across sources (real world data and study data).

Information from the tokenization procedure will not be reported in the clinical study report.

11.9. Study Visits and Assessments

See [Table 2](#), for a summary of procedures at each study visit. See [Section 11.1](#) to [Section 11.7](#) for detailed information on conducting assessments.

It is suggested that rating scales be completed in the following sequence, if possible. If the sequence must be changed, it is strongly suggested to complete the CGI-S and CGI-I scales after the other clinician-rated scales. The Investigator is encouraged to maintain the same sequence across visits for individual subjects.

Screening Visit (V1)	Baseline (V2) to Visit 10 (V10) Assessments will be collected at each visit as specified in Table 2	Visit 11 (V11) (Week 9 / Follow-up)
1. SCID-5-CT	1. PANSS	1.C-SSRS
2. PANSS	2. BNSS	
3. C-SSRS	3. C-SSRS	
4. CGI-S	4. SAS/BARS/AIMS	
	5. PSP	
	6. Healthcare resource utilization (HRU)	
	7. CGI-S	
	8. CGI-I	
	9. PSQI	
	10. SF-12	
	11. MSQ	

Note: Rating assessments will be performed by the rater or subject using an electronic tablet. In the event that the electronic tablet is not available or assessment not available on the tablet, the rating assessments will be performed by the rater or subject using a paper version of the assessment. SCID-5-CT will be performed using a paper version.

11.9.1. Screening: Visit 1 (Day -21 to -1)

After a subject provides consent, a unique subject number will be assigned at screening by the RTSM system, consisting of a 3-digit protocol number, 3-digit site number, and a unique 3-digit subject identifier (eg, the second screened subject from site #006 will be 308006002). Subjects will be numbered consecutively. No subject numbers are to be reused once assigned. This number will track a subject throughout their participation in the study and the open-label extension (OLE) study.

Subjects will be evaluated at the Screening Visit to determine their eligibility for the study. Screening assessments may occur over multiple days. The subject's eligibility assessment will be reviewed by the sponsor and/or designee based on protocol specified inclusion and exclusion criteria. In the event the sponsor/designee and site do not agree on a subject's eligibility then the subject will not be enrolled.

Subjects found to be ineligible during Visit 1 will not be required to complete all the Visit 1 assessments and will not be followed up on leaving the study.

Subjects who screen fail may be re-screened up to two times, if judged appropriate by the Investigator, after discussion with the Medical Monitor. Re-screened subjects will be re-consented, assigned a new subject number, and all Visit 1 procedures will be repeated.

The Screening Period may be extended for up to 7 days after approval from the Medical Monitor.

The following procedures will be conducted during this visit:

- Obtain signed informed consent and privacy authorization (if applicable or required by local law) from the subject before conducting any other visit procedures
- Obtain informed consent for duplicate subject check

CCI

- Review inclusion and exclusion criteria
- Collect prior and concomitant medications
- Obtain demographic information
- Collect medical history
- Collect psychiatric history
- Collect nicotine use information
- SCID-5CT
- Physical and neurological examination including height and weight; clinical site staff to calculate and record BMI
- Vital sign measurements
- 12-lead ECG
- Blood samples for clinical laboratory evaluation (hematology and serum chemistry). If possible, subjects should fast for at least 8 hours prior to avoid potential for retest.
- Blood samples for serum pregnancy test (serum human chorionic gonadotropin [β hCG]) for female subjects and serum follicle stimulating hormone (FSH) for post-menopausal women or if menopause is suspected
- Blood sample for hepatitis screening
- Urine sample for urinalysis and urine drug screen (UDS)
- PANSS
- CGI-S
- C-SSRS
- Collect adverse events (Note: events occurring prior to first dose of study drug will be identified programmatically as pretreatment events.)
- Duplicate subject check (where local regulations allow)
- Obtain signed consent for optional Tokenization
- Obtain confirmation of subject's eligibility through formal review process (Inclusion Criterion 20).

11.9.2. Pre-switch (PS) Baseline: Visit 2 (Day 1) – Treatment Period

The following procedures will be conducted during this visit:

CCI

- Review inclusion and exclusion criteria
- Collect concomitant medications
- Vital sign measurements
- Weight and waist circumference (BMI derived in the electronic data system)
- Perform standard 12-lead ECG
- Fasted blood samples for clinical laboratory evaluation (hematology and serum chemistry)
- Blood sample for POPPK

CCI

- Urine sample for urinalysis, UDS, and β hCG (for female subjects)
- PANSS
- CGI-S
- BNSS
- PSQI
- C-SSRS
- SAS
- BARS
- AIMS
- SF-12
- MSQ
- PSP
- HCRU (last 3-month lookback)
- Collect adverse events (Note: events occurring prior to first dose [on Day 1] of study drug will be identified programmatically as pretreatment events.)
- Dispense study drug

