Informed consent will be obtained from each subject before any study procedures are performed. Subjects will be evaluated for eligibility during a Screening Period of up to 21 days, during which they will continue on their pre-switch antipsychotic medication while being tapered off any prohibited medications ([Section 10.3.2](#)) in a manner that is consistent with labeling recommendations and conventional medical practices. Non-prohibited psychotropic medications other than the pre-switch antipsychotic may be continued during the study but must have been stable for at least 6 weeks prior to Screening and should be maintained at a stable dose and regimen (see [Section 10.3.1](#)).

Subjects who are being treated with two antipsychotic medications will be permitted to enter the Screening Period. At the start of Screening, the Investigator will determine which antipsychotic medication is considered “primary”, and the other one will be tapered off during the Screening Period.

Subjects who screen fail may be re-screened twice, if judged appropriate by the Investigator after discussion with the Medical Monitor. Re-screened subjects will be re-consented, assigned a new subject number, and all Visit 1 procedures will be repeated.

Open-label Treatment Period (8 weeks):

At Baseline (Day 1) (pre-switch [PS] Baseline), subjects who have successfully completed Screening and have met the eligibility criteria will begin open-label treatment with SEP-363856 while continuing to take the full dose of their pre-switch antipsychotic. SEP-363856 dosing will begin the evening of the PS Baseline visit and will continue once-daily, in the evening at bedtime, for the remainder of the Treatment Period, during which the procedures outlined in [Table 2](#) will be conducted. Subjects will be evaluated at PS Baseline and weekly throughout the rest of the study. [Section 10.3](#) describes the circumstances and specifications for which prior and concomitant psychotropic medications other than the pre-switch antipsychotic are allowed in this study.

Subjects will receive SEP-363856 50 mg/day from Day 1 through Day 3 and 75 mg/day from Day 4 through Day 7. Every effort should be made to maintain subjects at 75 mg/day from Day 4 through Day 7. Beginning on Day 8, the dose of SEP-363856 can be adjusted in increments of 25 mg among 3 dose levels (50, 75 and 100 mg), according to the following requirements:

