12. Subjects taking two antipsychotic medications (but not more) at screening are eligible for study inclusion, provided the total daily dose is equivalent to ≤ 12 mg/day haloperidol. However, the antipsychotic medication determined to be "secondary", based on Investigator judgment, must be discontinued prior to receiving SEP-363856. All subjects must be on a single antipsychotic medication at study baseline (Day 1).
13. Subject's body mass index (BMI) must be 18 kg/m² to 40 kg/m² (inclusive) at Screening.

14. For subjects taking nonpsychotropic medications for treating allowed chronic medical conditions, the dose and regimen must have been stable ($\pm 25\%$ total daily dose) for at least 30 days prior to screening.
15. Female subjects of childbearing potential must have a negative serum pregnancy test at Screening.
16. Female subjects of childbearing potential must agree to use acceptable effective and reliable contraception throughout the study and for at least 30 days after the last dose of study drug has been taken. In the Investigator's judgment, the subject will adhere to this requirement. Details on contraception requirement are provided in [Section 10.4](#).
17. Male subjects must agree to avoid fathering a child and to use acceptable effective methods of birth control from screening until at least 30 days after the last study drug administration. Details on contraception requirement are provided in Section 10.4.
18. Subject is, in the opinion of the Investigator, generally healthy based on screening medical history, physical examination (PE), neurological examination, vital signs, electrocardiogram (ECG) and clinical laboratory values (hematology, chemistry and urinalysis).
19. Subject has a stable living arrangement at the time of Screening and anticipates stable living arrangement for the duration of the study.
20. Subject's eligibility confirmed through formal review process (See [Section 10.6](#)).

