10.4. Contraception Requirements

Female subjects who participate in this study must be of:

- Non-childbearing potential (ie, physiologically incapable of becoming pregnant), which includes:
 - Women who have had a hysterectomy, bilateral oophorectomy, bilateral salpingectomy, bilateral tubal ligation or bilateral tubal occlusion (as determined by subject's medical history)

OR
 - Postmenopausal females, defined as at least 12 months of spontaneous amenorrhea and confirmed by follicle stimulating hormone (FSH) concentrations within postmenopausal range as determined by the central laboratory

-OR-

- Childbearing potential with a negative serum pregnancy test at screening and satisfying one of the following requirements:
 - Completely abstinent from intercourse as part of the preferred and usual lifestyle of the subject. Periodic abstinence (eg, calendar, ovulation, symptothermal, post-ovulation methods) and the withdrawal method are not acceptable methods of contraception. Subject must have been abstinent for at least 60 days prior to administration of the first dose of study drug, throughout the Treatment Period and for a minimum of 30 days after completion or premature discontinuation from the study drug.
 - Exclusively in a same sex relationship (if this is the subject's usual lifestyle choice). Subject must have been exclusively engaging in same sex relations for at least 60 days prior to administration of the first dose of study drug, throughout the Study and for a minimum of 30 days after completion or premature discontinuation from the study drug.
 - Use of acceptable effective methods of contraception during the Treatment Period and for 30 days after last dose of study drug. Acceptable effective forms of contraception include:
 - Subcutaneous hormonal implant (such as Norplant®) implanted at least 90 days prior to Screening;

- Injectable hormonal contraception (such as medroxyprogesterone acetate injection) given at least 14 days prior to Screening;
- Oral or transdermal hormonal contraception used as directed for at least 30 days prior to Screening.
- Vaginal ring (eg, NuvaRing[®]) used as directed for at least 30 days prior to Screening.
- Intrauterine device implanted at least 30 days prior to Screening.
- Intrauterine hormone-releasing system implanted at least 30 days prior to Screening.

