11.4.2. Clinical Laboratory Tests

The clinical laboratory tests required by protocol are listed in [Section 23](#), Appendix IV.

Blood and urine samples will be collected for clinical laboratory tests. For detailed instructions regarding clinical laboratory procedures, sampling, and shipping guidelines refer to the Central Laboratory Instructions Manual. Samples will be processed at a central laboratory to ensure consistency. All clinical laboratories will be College of American Pathologists (CAP), Clinical Laboratory Improvement Amendments (CLIA) (or equivalent) certified.

Point of care rapid testing will be used for the rapid urine pregnancy test and rapid urine drug test.

Clinically significant laboratory assessment at Screening will be captured in the medical history in the CRF. Any clinically significant changes from Screening, as determined by the Investigator, will be noted as AEs in the CRF. Positive drug screen findings observed during study participation must be discussed with the Medical Monitor to assess and determine subject disposition.

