11.9.8. Visit 8 (Week 6; Day 43 \pm 2 days) – Treatment Period

The following procedures will be conducted during this visit:

- Collect concomitant medications
- Vital sign measurements
- PANSS
- CGI-S
- CGI-I
- C-SSRS
- Collect adverse events

- Study drug accountability
- Dispense study drug

11.9.9. Visit 9 Telephone Contact (Week 7; Day 50 ± 2 days) – Treatment Period

The following procedures will be conducted during this visit:

- Collect concomitant medications
- C-SSRS
- Collect adverse events

11.9.10. Visit 10, End of Treatment (EOT) or Early Termination (ET) - (Week 8; Day 57 ± 2 days)

The following procedures will be conducted during this visit:

- Collect concomitant medications
- Collect nicotine use information
- Physical and neurological examination
- Vital sign measurements
- Weight and waist circumference (BMI derived in the electronic data system)
- Perform standard 12-lead ECG
- Fasted blood samples for clinical laboratory evaluation (hematology and serum chemistry) and β -hCG (for female subjects)
- Blood sample for POPPK
- Urine sample for urinalysis, rapid urine β -hCG (females), rapid urine drug screen, and UDS
- PANSS
- CGI-S
- CGI-I
- BNSS
- PSQI
- C-SSRS
- SAS
- BARS
- AIMS
- SF-12
- MSQ

- PSP
- HCRU (since last visit)
- Collect adverse events
- Study drug accountability
- Duplicate subject check

At this visit, subjects who have participated throughout the duration of the Treatment Period, up to and including Week 8 will have the option to enroll and continue treatment in an open-label extension study (Study SEP361-309).

For subjects entering the extension study, the Week 8 Visit in this study (SEP361-308) will serve as the OLE Baseline visit for the extension study (SEP361-309) and subjects will not need to return for further visits in this study.

Subjects who do not enter the extension study will complete the Follow-up Period.

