16.2. Computerized Systems Used for Source Data

A list of the computerized systems that will be used to create, modify, maintain, archive, retrieve, or transmit source data are presented below, pursuant to the Guidance for Industry Computerized Systems Used in Clinical Investigations, May 2007.

Table 6: Computerized Systems Used for Source Data

Protocol Step	Computerized System Type or Description
Informed consent	A
Review inclusion/exclusion criteria	A
Prior/concomitant medication review	A
Dispensation of study drug	F
Study drug accountability	A, F
Demography	A
Medical history	A
Psychiatric history	A
Nicotine use information	A
SCID-5-CT	none
Physical and neurological examination	A
Height	A
Vital signs	A
Weight (including BMI)	A
Waist circumference	A
12-lead Electrocardiogram (ECG)	B
Hematology, chemistry, and urinalysis	G
Blood sample for hepatitis	G
Serum follicle stimulating hormone (FSH)	G
Serum human chorionic gonadotropin (β -hCG), (females)	G

Table 6: Computerized Systems Used for Source Data (Continued)

Protocol Step	Computerized System Type or Description
CCI	
Blood sample for POPPK	C
Urine drug screen	G
Rapid urine drug screen	A
Urine β-hCG (females)	G
Rapid urine β-hCG (females)	A
Positive and Negative Syndrome Scale (PANSS)	D
Clinical Global Impression – Severity (CGI-S)	D
Clinical Global Impression – Improvement (CGI-I)	D
Brief Negative Symptom Scale (BNSS)	D
Pittsburgh Sleep Quality Index (PSQI)	D
Columbia Suicide Severity Rating Scale (C-SSRS)	D
Simpson-Angus Scale (SAS)	D
Barnes Akathisia Rating Scale (BARS)	D
Abnormal Involuntary Movement Scale (AIMS)	D
SF-12	D
Medication Satisfaction Questionnaire (MSQ)	D
Personal and Social Performance Scale (PSP)	D
Healthcare Resource Utilization (HCRU)	D
Pretreatment/Adverse events (AE) monitoring	A
Duplicate Subject Check	E
Tokenization consent (optional)	A
Tokenization, if consent signed	H

A = EDC (Medidata RAVE); B =ECG central vendor; C = LIMS/ American Standard Code for Information Interchange (ASCII); D = Signant Health; E = Verified Clinical Trials; F = Randomization and Trial Supply Management System (RTSM); G = Central Laboratory; H = Datavant.

Abbreviations: EDC = electronic data capture; LIMS = laboratory information management system; SCID-5-CT = Structured Clinical Interview for DSM-5, Clinical Trials Version.

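### The protocol neither requires nor ensures a negative Baseline pregnancy result before study drug is dispensed

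*Protocol*

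**What the plan says.** - **Eligibility.** Inclusion 15 (Section 8.1) reads "Female subjects of childbearing potential must have a negative serum pregnancy test at Screening". Section 10.4 also names only the Screening serum test. Exclusion 12 (Section 8.2) bars pregnant or lactating women and gives no test and no time point.
- **Visit 2.** Section 11.9.2 repeats the eligibility review, lists "Urine sample for urinalysis, UDS, and β hCG (for female subjects" as the only item with a pregnancy test, and ends with dispensing. Section 7.1 adds: "SEP-363856 dosing will begin the evening of the PS Baseline visit".
- **Where each test is read.** Table 6 (Section 16.2) has two separate rows, "Urine β-hCG (females) G" and "Rapid urine β-hCG (females) A". Code G is the central laboratory and code A is the site's electronic data capture. Section 11.4.2 states: "Point of care rapid testing will be used for the rapid urine pregnancy test and rapid urine drug test".
- **When the rapid test is done.** Among the visit lists in Section 11.9 it appears only at Visit 10 (Section 11.9.10): "Urine sample for urinalysis, rapid urine β -hCG (females), rapid urine drug screen, and UDS".
- **If a test is positive.** Table 2, footnote m, calls for serum confirmation of a positive urine test. Section 12.4.2 covers stopping study drug and retesting once a pregnancy is reported.

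**The concern.** Exclusion 12 is meant to hold at the moment of first exposure, and the protocol looks at it again on Day 1. The one Day 1 test that could inform that review goes to the central laboratory, while drug is handed out at the same visit. No passage says to wait for the result. A woman who conceived during Screening, or whose pregnancy was too early to detect then, could meet the criteria as they are applied and take an investigational drug alongside her full-dose pre-switch antipsychotic. The same-day test that would make the criterion checkable is already in the protocol, but it is placed at the end of treatment and not at first exposure.

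**Working it through.** **Age of the last test that eligibility requires.** SAP Section 6.1 computes a pre-dose study day as assessment date minus first-dose date, so there is no Day 0.

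- Screening runs from Day -21 to Day -1 (Section 11.9.1). Shortest gap to Day 1: 1 day. Longest gap: 21 days.
- The Medical Monitor may approve an extension of up to 7 days: 21 + 7 = 28 days.

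The Screening serum test is therefore 1 to 21 days old at first dose, or up to 28 with the extension. The figures 21 and 28 are maxima, not typical values. Screening can be shorter, its assessments may be spread over several days, and re-screening repeats all Visit 1 procedures.

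**Whether the Visit 2 result precedes the first dose.** The documents give no turnaround, so this has to be an assumption. Doses are taken once each evening from Day 1. If the result reaches the site during the day on Day 1 + k, then k doses have been taken. For an assumed k of 0 to 3, that is 0 to 3 doses. The text allows k = 0 but does not secure it.

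**How other Baseline conditions are written.** CGI-S and PANSS limits apply at Screening and Baseline (inclusions 6 and 7). Suicidal ideation is an exclusion at Screening or Baseline (exclusion 5), and so is raised blood pressure (exclusion 13). All of these are obtained at the site during the visit. Pregnancy has a Baseline sample but no Baseline criterion and no on-site reading. The sponsor's eligibility review (Sections 10.6 and 11.9.1) belongs to Screening and does not cover the Visit 2 sample.

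**Contraception during Screening.** Section 10.4 introduces the female methods with "Use of acceptable effective methods of contraception during the Treatment Period and for 30 days after last dose of study drug", whereas inclusion 16 covers the whole study. Lead times by method:

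- Implant: at least 90 days before Screening.
- Injectable: at least 14 days before Screening.
- Oral, transdermal, ring, intrauterine device or hormone-releasing system: at least 30 days before Screening.
- Abstinence or an exclusively same-sex relationship: at least 60 days before first dose, which exceeds 28 days and so covers Screening.
- Two barrier methods: no lead time.

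The mismatch therefore matters mainly for the two-barrier option.

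**Effect on the endpoints.** Section 13.1 lists pregnancy as its own discontinuation reason, and Section 12.4.2 does not ordinarily treat it as an adverse event. A case would stay out of the primary endpoint and count in the secondary one. With the 101 enrolled subjects in SAP Section 3.4, one case is 1/101 = 0.99 percentage points.

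**The case against.** Inclusion 15 and Section 10.4 agree with each other, so the eligibility rule is consistent as written. Exclusion 12 has no time limit and is re-reviewed at Visit 2, so a known positive excludes the subject. Positive urine tests go to serum confirmation, and Section 12.4.2 acts quickly once a pregnancy is known. Table 6 records where source data originate, not when a result reaches the site, and Section 11.4.2 leaves laboratory procedure to a manual outside these documents.

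Much of this stands, and it rules out three stronger readings:

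- A reader might infer that pregnancy cannot be ruled out before dosing. The documents do not support that: turnaround is unstated and the first dose is at bedtime.
- A reader might infer undetected exposure until the next scheduled test at Day 29. That does not follow either, because the Visit 2 sample itself yields a result.
- A reader might want an expected number of cases. The documents give neither the number of women of childbearing potential nor a conception rate. A count of conceptions would also overstate the benefit, because a urine test misses very recent ones.

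What the objection does not answer is the timing. Serum confirmation and Section 12.4.2 both start from a known positive, and neither makes the Visit 2 result available before drug is handed out. Redacted items adjoin the Visit 2 list, but the pregnancy-test rows are legible and nothing suggests another one.

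**Conclusion.** The point holds as a gap in what the protocol requires. A negative Baseline pregnancy result is neither demanded nor ensured before dispensing, so exclusion 12 may rest on a Screening serum test up to 21 days old, or 28 with the extension. This rests on reading Table 6 with Section 11.4.2 to mean that the ordinary urine test is processed centrally. If the laboratory manual secures a result before the Day 1 dose, the practical risk disappears and only the wording needs correcting. The risk is rare and no planned estimate is biased. It is worth correcting because the consequence is serious and the remedy is nearly free.

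One related inconsistency needs settling in any case: SAP Section 17.4 lists the rapid urine pregnancy test among central-laboratory results, while Protocol Section 11.4.2 and Table 6 place it at the point of care. Since the SAP reports enrolment of 101 subjects, an amendment may come too late for this cohort. The correction would then serve any reuse of the protocol text.

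**What to change.** 1. In Table 2 and Section 11.9.2, schedule the existing rapid urine β-hCG on the urine already collected at Visit 2, so that the result is available at the Visit 2 eligibility review and before dispensing.
2. Reconcile inclusion 15 and exclusion 12 with that timing, so that the text states which result the Visit 2 review relies on.
3. Reconcile the contraception period in Section 10.4 with inclusion 16, with attention to the two-barrier option.
4. Reconcile SAP Section 17.4 with Protocol Section 11.4.2 and Table 6 on where the rapid test is read.

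Cost: one rapid kit per female subject at Visit 2, of a type already needed for Visit 10, plus wording changes. No extra visit, sample or blood draw is needed, and no analysis changes.
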